### 2.1. Study Design

*This will be a Phase 1, open-label, parallel-group study to investigate the effect of severe hepatic impairment on the plasma PK, safety and tolerability after a single oral 30 mg dose of dacomitinib under fasted conditions.*

*At Screening, the modified Child-Pugh classification score as outlined in Appendix 8 of the Protocol will be utilized to assess entry criteria and to assign participants into the appropriate hepatic impairment group (Table 1 below). The modified Child-Pugh classification criteria will permit enrollment of participants with a history of Stage 3 or Stage 4 encephalopathy who are receiving medication(s) to prevent recurrent encephalopathy; participants with clinically active Stage 3 or 4 encephalopathy will be excluded from participation in the study. The criteria will also allow enrollment of participants with history of severe ascites who are on medication(s) to control their ascites.*

**Table 1. Hepatic Function Categories Based on Child-Pugh Classification**

Cohort	Description	Child-Pugh Score	Number of Participants
1	Severe hepatic impairment	Class C (10 to 15 points)	8
2	Normal hepatic function	Not applicable	8 a

a. Participants in Cohort 2 may be dosed to a maximum of 10 participants to ensure that the age of each participant in Cohort 2 is within <math>\pm 10</math> years and the body weight is within <math>\pm 15</math> kg to the median age and median body weight of participants in Cohort 1, respectively.
			

Approximately 18 participants will be enrolled into the study to ensure at least 6 PK evaluable (having data for estimating primary PK parameters for dacomitinib) participants in each cohort. Participants who withdraw may be replaced upon agreement with the Sponsor.

The participants from the severely impaired hepatic function cohort will be recruited first, and a median value for age and weight will be determined for all evaluable participants across study sites in this cohort. Then the control participants from the normal hepatic function cohort will be recruited later such that the age of each participant in Cohort 2 is within  $\pm 10$  years and the body weight is within  $\pm 15$  kg of the median of the participants in the severe hepatic impairment cohort (Cohort 1). An attempt will be made to maintain a similar male/female ratio and racial make-up between Cohorts 1 and 2. Approval from the Sponsor must be obtained **before** proceeding with dosing participants in Cohort 2.

After the PK data from all participants with severe hepatic impairment (Cohort 1) have been reviewed, the Sponsor will notify the site if additional participants for Cohort 1 are required. If no additional participants are required, recruitment for participants with normal hepatic function (Cohort 2) will begin. If the PK variability is greater than expected, additional participants may be enrolled in Cohort 1 and the sample size for Cohort 2 will also be increased accordingly.

The end of the study is defined as the date of the last visit of the last participant in the study.

[figure not shown]
## 2.2. Study Objectives

### **Primary Objective**

To evaluate the effect of severe hepatic impairment on the single dose plasma PK of dacomitinib.

### **Secondary Objective**

To assess the safety and tolerability of a single oral dose of dacomitinib in participants with normal hepatic function and participants with severe hepatic impairment.

### **Tertiary/Exploratory Objectives**

- *To characterize the effect of severe hepatic impairment on other plasma PK parameters of dacomitinib and its metabolite PF-05199265.*
- *To analyze CYP2D6 genotype in pharmacogenetic samples.*
- *To enable exploratory research through collection of banked biospecimens, unless prohibited by local regulations or ethics committee decision.*

### **3. INTERIM ANALYSES, FINAL ANALYSES AND UNBLINDING**

No formal interim analysis will be conducted for this study. As this is an open-label study, the Sponsor may conduct unblinded reviews of the data during the course of the study for the purpose of safety assessment, facilitating dose selection decisions, and/or supporting clinical development.

Final analysis will follow the official database release. As this will be an open-label study, there is no formal unblinding of the randomization code.

### **4. HYPOTHESES AND DECISION RULES**

#### **4.1. Statistical Hypotheses**

No hypotheses are required.

#### **4.2. Statistical Decision Rules**

No decision rules are required.

### **5. ANALYSIS SETS**

#### **5.1. Pharmacokinetic (PK) Analysis Set**

##### **5.1.1. Concentration Analysis Set**

This set is defined as *all participants who take 1 dose of dacomitinib and have at least 1 dacomitinib plasma concentration.*

##### **5.1.2. Parameter Analysis Set**

This set is defined as *all participants who take 1 dose of dacomitinib and have at least 1 dacomitinib plasma PK parameters of primary interest.*

#### **5.2. Pharmacodynamic Analysis Set**

None.

### **5.3. Safety Analysis Set**

This set is defined as *all participants assigned to dacomitinib and who take 1 dose of dacomitinib*.

### **5.4. Other Analysis Sets**

None.

### **5.5. Treatment Misallocations**

All analyses will be performed on an “as-treated” basis and will not include data from subjects who are randomized but not treated.

If a subject takes a treatment out of sequence or takes the same treatment twice, then they will be reported under the treatment that they actually receive for all safety, PK and pharmacodynamic analyses, where applicable.

### **5.6. Protocol Deviations**

Subjects who experience events that may affect their PK profile (e.g. lack of compliance with dosing) may be excluded from the PK analysis. At the discretion of the pharmacokineticist a concentration value may also be excluded if the deviation in sampling time is of sufficient concern or if the concentration is anomalous for any other reason.

A full list of protocol deviations will be compiled and reviewed to identify major and minor deviations prior to database closure.

#### **5.6.1. Deviations Assessed Prior to Randomization**

At Screening, the investigator will assess subjects against the inclusion and exclusion criteria as set out in Sections 5.1 and 5.2 of the protocol.

#### **5.6.2. Deviations Assessed Post-Randomization**

A full list of protocol deviations for the study report will be compiled prior to database closure. Any significant deviation from the protocol will be reviewed prior to database closure and a decision taken regarding evaluation for each analysis population.

## **6. ENDPOINTS AND COVARIATES**

### **6.1. Efficacy Endpoint(s)**

None.

## 6.2. Safety Endpoints

Any events occurring following start of treatment or increasing in severity will be counted as treatment emergent.

Events that occur in a non-treatment period (for example, Washout or Follow-up) will be counted as treatment emergent and attributed to the previous treatment taken.

The following data are considered in standard safety summaries (see protocol for collection days and list of parameters):

- *adverse events;*
- *laboratory data;*
- *vital signs data;*
- *ECG results.*

## 6.3. Other Endpoints

### 6.3.1. PK Endpoints

Blood samples for PK analysis of dacomitinib and PF-05199265 will be taken according to the Schedule of Activities given in the protocol.

The following PK parameters will be calculated for dacomitinib and PF-05199265 (if possible) from the concentration-time data using standard noncompartmental methods:

**Table 2. Noncompartmental PK Parameters**

PK Parameter	Analysis Scale	Dacomitinib	PF-05199265
$AUC_{inf}^*$	ln	A, D	A, D
$AUC_{inf,u}^*$	ln	A, D	A, D
$AUC_{last}$	ln	A, D	A, D
$AUC_{last,u}$	ln	A, D	A, D
$C_{max}$	ln	A, D	A, D
$C_{max,u}$	ln	A, D	A, D
$T_{max}$	R	D	D
$t_{1/2}^*$	ln	D	D
$CL/F^*$	ln	D	-
$CL_u/F^*$	ln	D	-
$V_z/F^*$	ln	D	-
$V_{z,u}/F^*$	ln	D	-
Fu	R	D	D

Key: A=analyzed using statistical model, D=displayed with descriptive statistics, ln=natural-log transformed, R=raw (untransformed), u=unbound, \*=if data permits

### 6.3.2. PD Endpoints

None.

### 6.4. Covariates

None.

## 7. HANDLING OF MISSING VALUES

For the analysis of safety endpoints, the sponsor data standard rules for imputation will be applied.

### 7.1. Concentrations Below the Limit of Quantification

In all data presentations (except listings), concentrations below the limit of quantification (BLQ) will be set to zero. (In listings BLQ values will be reported as “<LLQ”, where LLQ will be replaced with the value for the lower limit of quantification).

### 7.2. Deviations, Missing Concentrations and Anomalous Values

In summary tables and plots of median profiles, statistics will be calculated having set concentrations to missing if 1 of the following cases is true:

1. A concentration has been collected as ND (ie, not done) or NS (ie, no sample);

2. A deviation in sampling time is of sufficient concern or a concentration has been flagged anomalous by the pharmacokineticist.

Note that summary statistics will not be presented at a particular time point if more than 50% of the data are missing.

### 7.3. Pharmacokinetic Parameters

Actual PK sampling times will be used in the derivation of PK parameters.

If a PK parameter cannot be derived from a subject's concentration data, the parameter will be coded as NC (ie, not calculated). (Note that NC values will not be generated beyond the day that a subject discontinues).

In summary tables, statistics will be calculated by setting NC values to missing; and statistics will be presented for a particular hepatic function group with  $\geq 3$  evaluable measurements. For statistical analyses (ie, analysis of variance), PK parameters coded as NC will also be set to missing; and analyses will not be performed for a particular parameter if more than 50% of the data are NC.

If an individual subject has a known biased estimate of a PK parameter (due for example to an unexpected event such as vomiting before all the compound is adequately absorbed in the body), this will be footnoted in summary tables and will not be included in the calculation of summary statistics or statistical analyses.

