impairment (Child-Pugh Class B, score 7-9, n = 9), and a control group of healthy participants with normal hepatic function (n = 8). The results showed that the mean fraction of dacomitinib unbound in plasma ( $f_u$ ) was identical across the 3 groups ( $f_u = 0.02$ ). The mean (percent coefficient of variation [%CV])  $f_u$  of PF-05199265 was 0.00011 (28%), 0.00016 (69%), and 0.00025 (62%) for participants with normal hepatic function, mild hepatic impairment, and moderate hepatic impairment, respectively. Results also showed that mild hepatic impairment status did not alter dacomitinib plasma exposures and that moderate hepatic impairment status reduced dacomitinib plasma exposures ( $AUC_{inf}$  and  $C_{max}$  by 15% and 20%, respectively) as compared to normal hepatic function. These changes are not considered clinically significant and no starting-dose adjustment is currently recommended for patients with mild or moderate hepatic impairment. In addition, a single oral 30 mg dose of dacomitinib was well tolerated in participants with mild or moderate impaired hepatic function. No participants in the normal hepatic function group or the mild hepatic impairment group experienced an AE. One (1) participant in the moderate hepatic impairment group died due to a road traffic accident. This death was classified as a serious adverse event (SAE) and was considered to be severe but was not treatment-related. There were no laboratory safety tests, vital signs results, or electrocardiogram (ECG) results of clinical concern.

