**Table 3. PK Parameters to be Summarized Descriptively by Group**

Parameter	Summary Statistics
$AUC_{inf}$ , $AUC_{inf,u}$ , $AUC_{last}$ , $AUC_{last,u}$ , $C_{max}$ , $C_{max,u}$ , $CL/F$ , $CL_u/F$ , $V_z/F$ , and $V_{z,u}/F$	N, arithmetic mean, median, cv%, standard deviation, minimum, maximum, geometric mean and geometric cv%.
$T_{max}$	N, median, minimum, maximum.
$t_{1/2}$ , $t_u$	N, arithmetic mean, median, cv%, standard deviation, minimum, maximum.

Supporting data from the estimation of  $t_{1/2}$  and  $AUC_{inf}$  will be listed by analyte and group: terminal phase rate constant ( $k_{el}$ ); goodness of fit statistic from the log-linear regression ( $r^2$ ); the percent of  $AUC_{inf}$  based on extrapolation ( $AUC_{extrap\%}$ ); and the first, last, and number of time points used in the estimation of  $k_{el}$ . This data may be included in the clinical study report.

Presentations for dacomitinib and PF-05199265 concentrations will include:

- a listing of all concentrations sorted by hepatic function group (present in heading), subject id and nominal time postdose. The concentration listing will also include the actual times. Deviations from the nominal time will be given in a separate listing.
- a summary of concentrations by hepatic function group and nominal time postdose, where the set of statistics will include n, mean, median, standard deviation, coefficient of variation (cv), minimum, maximum and the number of concentrations above the lower limit of quantification.
- median concentrations time plots (on both linear and semi-log scales) against nominal time postdose by hepatic function group (all hepatic function groups on the same plot per scale, based on the summary of concentrations by hepatic function group and time postdose).
- mean concentrations time plots (on both linear and semi-log scales) against nominal time postdose by hepatic function group (all hepatic function groups on the same plot per scale, based on the summary of concentrations by hepatic function group and time postdose).
- individual concentration time plots by hepatic function group (on both linear and semi-log scales) against actual time postdose (there will be separate spaghetti plots for each hepatic function group per scale).
- Box and whisker plots for individual subject parameters ( $AUC_{inf}$ ,  $AUC_{inf, u}$ ,  $AUC_{last}$ ,  $AUC_{last, u}$ ,  $C_{max}$ , and  $C_{max, u}$ ) by hepatic function group and overlaid with geometric means.

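### Could the SAP's 50% limit on non-calculable PK parameters let the ANOVA report a ratio for a cohort with only one or two values?

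*SAP*

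**What the plan says.** SAP 7.3 holds two rules for parameters coded NC. For summary tables, NC values are set to missing and "statistics will be presented for a particular hepatic function group with" at least 3 evaluable measurements. For the ANOVA, NC values are also set to missing, and "analyses will not be performed for a particular parameter if more than 50% of the data are NC". The first rule names its unit, the hepatic function group. The second names none.

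The surrounding text bears on how the second rule is read:

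- SAP 7.2 uses almost the same form for concentrations: "summary statistics will not be presented at a particular time point if more than 50% of the data are missing". The output it governs, listed in SAP 8.1 after Table 3, is "a summary of concentrations by hepatic function group and nominal time postdose".
- SAP 8.1 fits a one-way ANOVA on the log scale, restricted to CYP2D6 extensive and intermediate metabolizers (EM/IM), and carries out the comparisons only as far as the data allow. Appendix 1 contains no count check.
- SAP Table 2 (key: "A=analyzed using statistical model, D=displayed with descriptive statistics") marks six parameters for modelling in each of two analytes. Of these six, only AUCinf and AUCinf,u carry the asterisk for parameters that may not be derivable.
- SAP 2.1 states: "Approximately 18 participants will be enrolled into the study to ensure at least 6 PK evaluable" participants in each cohort, evaluability being defined on the primary dacomitinib parameters. After the Cohort 1 PK data are reviewed, "the Sponsor will notify the site if additional participants for Cohort 1 are required".
- SAP 4.1 and 4.2 state that there are no hypotheses and no decision rules.

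**The concern.** The ANOVA is one model fitted to both cohorts, so the data for a parameter could be taken to mean all values entering that model. On that reading, NC values confined to one cohort can be offset by a complete second cohort. A Test/Reference ratio and 90% CI could then appear for a cohort with one or two values, although the preceding sentence suppresses that cohort's summary statistics. With a single Test value, the residual variance comes entirely from the normal cohort, so the interval says nothing about variability in severe impairment.

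The target of 6 evaluable participants does not formally exclude this. It concerns the primary dacomitinib parameters, is not tied to the EM/IM subset, and is a recruitment aim rather than a condition for running the model.

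**Working it through.** **Inputs.** Cohort sizes are 8 and 8, with Cohort 2 extendable to 10 (SAP Table 1), and the target is at least 6 evaluable per cohort (SAP 2.1). The confidence level is 90% (SAP 8.1, Appendix 1). The enrolment figure of about 18 agrees with 8 + 10 = 18. It is not derived from power or precision, so there is no sample-size formula to reproduce. No CV for AUC or Cmax is given; 30% and 50% are assumed below.

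**1. What each reading allows.** The pooled share is k/(n1+n2), with k NC values all in Cohort 1. The per-cohort share is k/n1.

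| Sizes | NC in Cohort 1 | Pooled share | Model runs if pooled | Per-cohort share | Model runs if per cohort |
|---|---|---|---|---|---|
| 8 + 8 | 6 | 6/16 = 37.5% | yes, 2 values left | 75.0% | no |
| 8 + 8 | 7 | 7/16 = 43.8% | yes, 1 value left | 87.5% | no |
| 8 + 10 | 7 | 7/18 = 38.9% | yes, 1 value left | 87.5% | no |
| 6 + 6 | 5 | 5/12 = 41.7% | yes, 1 value left | 83.3% | no |
| 8 + 8 | 8 | 8/16 = 50.0% | not stopped, 0 values left | 100% | no |

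The last row is informative. Taken literally, a pooled limit would not stop a model in which the contrast cannot be estimated at all. The per-cohort limit leaves at least 4 of 8, 5 of 10 or 3 of 6.

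**2. Width of the interval if the pooled reading were used.** The limits around a ratio of 100% are exp(± t(0.95, n1+n2−2) × s × √(1/n1+1/n2)), with s = √ln(1+CV²). This gives s = 0.294 at CV 30% and 0.472 at CV 50%. Example, 1 v 8 at CV 30%: 1.895 × 0.294 × √1.125 = 0.590, and exp(±0.590) gives 55-180%.

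| Test v Reference | CV 30% | CV 50% |
|---|---|---|
| 4 v 8 | 72-139% | 59-169% |
| 2 v 8 | 65-154% | 50-200% |
| 1 v 8 | 55-180% | 39-258% |

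For comparison, 8 v 8 at CV 30% gives 77-130%. With equal log-scale variances these t-intervals keep their 90% coverage at any split. They become wide, not wrong.

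**3. Where many NC values could arise.** There are 6 × 2 = 12 modelled comparisons. Three are total dacomitinib Cmax, AUCinf and AUClast, the primary endpoints and their fallback. The other 9 are exploratory (Protocol Section 3). Of those 9, Table 2 flags 3 as possibly not derivable: dacomitinib AUCinf,u, and PF-05199265 AUCinf and AUCinf,u.

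For dacomitinib, half-lives of 54 to 80 h (Protocol 2.2.4) and sampling to 264 h give 264/80 = 3.3 to 264/54 = 4.9 half-lives. On a mono-exponential decline the extrapolated share is exp(−ln 2 × 264/t½), that is 3.4% to 10.2%. A longer half-life in severe impairment would raise this share, and Protocol Section 3 then provides the AUClast fallback. Dacomitinib AUCinf,u relies on the same terminal phase as total AUCinf. The documents give no NC rate for any parameter, so no probability can be attached to 6 or 7 NC values out of 8 in one cohort.

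**4. Which reading fits the text.** The sentence just before works by hepatic function group. The parallel 50% rule in SAP 7.2 governs a by-group summary. Nothing in either document describes a count over both cohorts.

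**The case for a change.** The strongest case for a change is that two competent programmers could implement the sentence differently, and that one added sentence would settle it. That is true as far as it goes: the denominator is not stated, and a clarification would cost almost nothing. It is also true that a per-cohort 50% limit is not a complete safeguard. If the EM/IM restriction left only 4 participants in a cohort, 2 of 4 NC is 50.0% and 2 values could still enter the model. That needs a cohort well below the target of 6, and the summary-table minimum of 3 in the same paragraph would already signal that it is too sparse.

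A second argument concerns coverage. In the study of mild and moderate impairment, the fraction unbound "of PF-05199265 was 0.00011 (28%), 0.00016 (69%), and 0.00025 (62%) for participants with normal hepatic function", mild and moderate impairment in that order, so variances may differ between cohorts. Suppose CVs of 62-69% carry over to severe impairment and are independent of total exposure, whose CV is taken as 30-50% in both cohorts. With 8 Reference values, simulated coverage of the 90% CI is then about 83-86% with 4 Test values and 71-81% with 1. This does not carry the point. The shortfall comes from applying a pooled variance to unequal variances in unbalanced cohorts. It would concern only the three unbound PF-05199265 comparisons, and the documents support neither assumption. Limiting NC values per cohort would still leave 80-86% with 3 or 4 Test values.

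**Conclusion.** The omission is real but does not call for a change. The natural reading, within each cohort, fits the neighbouring rules and keeps at least 4 of 8 or 3 of 6 values. Only a pooled reading, which the SAP nowhere states, lets a cohort of one or two values through. Even then the result would be an interval such as 55-180% (1 v 8, assumed CV 30%), with correct coverage under equal variances and plainly uninformative. The individual parameters are listed by group, so the sparse cohort would be visible. The comparisons where this is most conceivable are three exploratory ones, and no hypothesis or decision rule rests on any of them. SAP 8.1 also makes the ANOVA depend on what the data allow, so an analyst faced with one value is not obliged to fit it.

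This conclusion assumes that the analysts read the limit by cohort, or decline to model a cohort too small to summarise. It also rests on the absence of any NC rate in the documents that would make heavy one-sided loss likely.

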## 8. STATISTICAL METHODOLOGY AND STATISTICAL ANALYSES

### 8.1. Statistical Methods and Analyses

*The effect of hepatic impairment on PK parameters will be assessed by constructing 90% confidence intervals (CIs) around the estimated difference between the Test (severe hepatic impairment cohort; Cohort 1) and the Reference (normal hepatic function; Cohort 2) using a one-way analysis of variance (ANOVA) model based on natural log transformed data. Only participants with CYP2D6 EM and IM in each cohort will be included in this analysis.*

*One-way ANOVA will be used to compare the natural log transformed  $AUC_{inf}$ ,  $AUC_{last}$  and  $C_{max}$ , and  $AUC_{inf,u}$ ,  $AUC_{last,u}$  and  $C_{max,u}$  of dacomitinib and PF-05199265, as data permit, for severe hepatic impairment cohort (Test) to the normal hepatic function cohort (Reference). Estimates of the adjusted mean differences (Test-Reference) and corresponding 90% CIs will be obtained from the model. The adjusted mean differences and 90% CIs for the differences will be exponentiated to provide estimates of the ratio of adjusted geometric means (Test/Reference) and 90% CIs for the ratios as a percentage.*

The dacomitinib PK parameters ( $AUC_{inf}$ ,  $AUC_{inf,u}$ ,  $AUC_{last}$ ,  $AUC_{last,u}$ ,  $C_{max}$ ,  $C_{max,u}$ ,  $T_{max}$ ,  $t_{1/2}$ ,  $CL/F$ ,  $CL_u/F$ ,  $V_z/F$ , and  $V_{z,u}/F$ ) and PF-05199265 PK parameters ( $AUC_{inf}$ ,  $AUC_{inf,u}$ ,  $AUC_{last}$ ,  $AUC_{last,u}$ ,  $C_{max}$ ,  $C_{max,u}$ ,  $T_{max}$ ,  $t_{1/2}$ ) will be summarized descriptively by cohort. Boxplots of mean, median and individual participant parameters will be made by cohort for  $AUC_{inf}$ ,  $AUC_{inf,u}$ ,  $AUC_{last}$ ,  $AUC_{last,u}$ ,  $C_{max}$ , and  $C_{max,u}$ . Similar presentations will also be made for other PK parameters, if considered relevant. Dacomitinib and PF-05199265 total and unbound concentrations will be listed and summarized descriptively by PK sampling time and cohort. Summary profiles (means and medians) of the dacomitinib and PF-05199265 concentration-time data will be plotted by cohort on linear and semi-log scale. Individual participant concentration time profiles will be also presented. For summary statistics and summary plots by sampling time, the nominal PK sampling time will be used, for individual participant plots by time, the actual PK sampling time will be used.

[figure not shown]
Residuals from the models will be examined for normality and the presence of outliers via visual inspection of plots of residuals vs predicted values and normal probability plots of residuals but these will not be included in the clinical study report. If there are major deviations from normality or outliers then the effect of these on the conclusions will be investigated through alternative transformations and/or analyses excluding outliers. Justification for any alternative to the planned analysis will be given in the report of the study.

The following PK parameters will be summarized and listed by hepatic function group:

